Perfusion index (PI) is an assessment of the pulsatile strength at a specific monitoring site, and as such PI is an indirect and noninvasive measure of peripheral perfusion. It is calculated by means of pulse oximetry by expressing the pulsatile signal as a percentage of the nonpulsatile signal, both of which are derived from the amount of infrared (940 nm) light absorbed. The PI value is relative to a particular monitoring site, (e.g. the fingertip or toe), of each patient as physiological conditions vary between monitoring sites and individual patients.

Potential Benefits and Risks to Patients:

No foreseeable benefit can be expected on included patients.

Given the observational design and the well studied effects of continuous non-invasive infrared pulse oximetry monitoring we can reliably declare that we expect no possible harm to the patients included in the study.

Methods:

Study Design.

Double-blind study involving ninety two subjects treated with advanced life support according to the European Resuscitation Council (ERC) recommendations will be included in one observatory arms. Patient treatment during resuscitation will be determined by the treating clinician within the frame of ERC recommendations. Monitoring of perfusion index will be initiated as soon as possible and recorded until the end of the resuscitation efforts. ETCO₂ will be placed as soon as possible and recorded until the end of the resuscitation irrespectively if measured while the patient is ventilated through a bag-valve-mask or through a advanced infraglottic airway.

Study population and selection criteria.

All aspects of the study and consent forms will be approved by our Ethical Board prior to implementation. All patients in cardiac arrest, after application of the inclusion and exclusion criteria, with an indication to initiate an advanced life support will be included in the study. Included participants that will be successfully reanimated and that will regain a sufficient level of consciousness will be required to sign a full informed consent.

Inclusion criteria will be a cardiac arrest in a subject aged between 12 to 99 years old with an indication to start an ALS.

Subjects will be excluded from the study if younger than 12 years old, if pregnant or if prisoners at study inclusion.

We aim to recruit 90 patients in cardiac arrest for whom an ALS has been initiated.

Recruitment methods.

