All subjects that will be treated by the mobile intensive care unit of CHU Saint Pierre during study period will be screened for eligibility. Subjects having regained a sufficient neurological awareness to sign an informed consent for the study will review and undergo informed consent.

This study will be listed at www.clinicaltrials.gov.

Data collection and reporting.

Data will be collected throughout the intervention up until death or hospital admission or intensive care admission whichever comes first.

Expected outcomes.

It is the sponsor's expectation that higher perfusion index and upwards trends will be associated with higher chances of ROSC during ALS. Moreover, the sponsor expectation is that lower perfusion index following ROSC will be associated with higher chances of re-arrest. Finally the sponsor expect that a combined index including PI, ETCO₂ and rhythm would overperform each of these items in terms of capacity of predicting ROSC chances.

Adverse reactions.

There is no expectation of any adverse outcomes or reactions due to a patient being monitored with a Radical 97 monitor. Any adverse reactions should be reported immediately to the principal investigator or co-investigators

Reasons for Withdrawal or Termination

A subject may be discontinued from the study at any time if the subject, the Investigator, or the Sponsor feels that it is not in the subject's best interest to continue.

The following is a list of possible reasons for study treatment discontinuation:

- Screening Failure
- Subject withdrawal of consent
- The treating clinician is not compliant with study or ERC procedures
- Adverse Event that in the opinion of the Investigator would be in the best interest of the subject to discontinue study participation
- Protocol violation requiring discontinuation
- Mechanical – technical failure of the monitor

Handling of Participant Withdrawals of Termination:

Although subjects may withdraw from the study at any time and for any reason, (or may be withdrawn according to the abovementioned pre-specified cases), subject withdrawal should be avoided as much as reasonably possible.

Premature Termination or Suspension of Study:

This study may be temporarily suspended or prematurely terminated if there is sufficient reasonable cause. Written notification, documenting the reason for study suspension or termination, will be provided by the suspending or terminating party to the Investigator, and the Sponsor.

SAMPLE SIZE JUSTIFICATION

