Sample Size Calculations

We an expected sensitivity and specificity of 90% for PI to predict ROSC, an expected prevalence of ROSC of 40%, a precision of 10% and a type I error rate of 0.05 we calculated a required sample size of 87. Including a possible dropout of 5% we calculated a final sample size of 92.

STATISTICAL ANALYSIS PLAN

Primary Endpoint

We will determine the predictive value of PI measures for ROSC. We will calculate the sensitivity and specificity at multiple different PI thresholds along with corresponding 95% confidence intervals. Overall discrimination of PI for ROSC will be presented as area under the receiver operator characteristic curve (AUC/ROC). PI values will be averaged on two minutes. Each value will be tested for its ability to predict ROSC during the following ALS cycle (2 minutes). To assess the trending ability of PI to detect ROSC we will measure the difference (ΔPI) between initial PI and PI values of the cycle preceding ROSC or the last cycle in the absence of ROSC. We will then examine the association between ΔPI and ROSC through a multivariable logistic regression while adjusting for predetermined baseline confounders such as age, initial rhythm, noflow time, bystander CPR and sex.

Secondary Endpoints

Superiority analysis of PI compared to ETCO₂ in predicting ROSC. Initial and final values of both PI and ETCO₂ will be assessed for their ability to predict ROSC. Moreover averaged values per 2 min cycle will be assessed for their ability to predict ROSC in the following cycle. The constructed ROC curves will be compared using the algorithm suggested by De Long.

Tertiary Endpoints

As a tertiary endpoint we will study the predictive value of PI to predict further re-arrest following a ROSC. Overall discrimination of PI for re-arrest will be presented as area under the receiver operator characteristic curve (AUC/ROC). PI values will be averaged on two minutes. Each value will be tested for its ability to predict a re-arrest during the following 2 minutes.

ASSESSMENT OF SAFETY

Adverse events (AE) will be monitored and collected by the study team during the monitoring phase of the study. For each AE, a detailed explanation will be obtained from the treating physician and medical record. All AEs will be recorded on the CRFs.

Definition of Adverse Event

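### The ΔPI–ROSC regression does not name initial PI as a covariate, so its coefficient can mix the change in PI with the starting level

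*Protocol*

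**What the plan says.** The Primary Endpoint paragraph of the Protocol's STATISTICAL ANALYSIS PLAN section defines the trend measure as "the difference (ΔPI) between initial PI and PI values of the cycle preceding ROSC or the last cycle in the absence of ROSC". ROSC is then regressed on ΔPI in a multivariable logistic model, and the covariates are given by the words "adjusting for predetermined baseline confounders such as age, initial rhythm, noflow time, bystander CPR and sex". Five covariates are named. Initial PI is not one of them, and no other section adds it to this model. The words *such as* leave the list open.

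Four other places bear on the point:

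- Expected outcomes: the sponsor expects that "higher perfusion index and upwards trends will be associated with higher chances of ROSC during ALS".
- Product Description: "The PI value is relative to a particular monitoring site, (e.g. the fingertip or toe), of each patient as physiological conditions vary".
- Secondary Endpoints: "Initial and final values of both PI and ETCO₂ will be assessed for their ability to predict ROSC". Here initial PI is a predictor in its own right, not a covariate in the ΔPI model.
- Goals of the study: absolute PI values (goal 1) and the change in PI (goal 2) are separate questions.

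**The concern.** Initial PI is one of the two terms of ΔPI, so the two are generally correlated. If the starting level also carries information on ROSC, as the sponsor's expectation implies, initial PI is related to both the exposure and the outcome. A model without it gives a ΔPI coefficient that combines the effect of the change with part of the effect of the starting level. When a high start tends to go with a smaller rise, the two effects work against each other and the trend looks weaker than it is.

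What is at stake is goal 2, the association between change in PI and ROSC. The issue is separate from the time at which the later PI is read. It would remain if every patient were observed over the same interval.

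**Working it through.** **The plan's own figures.** Precision formula for sensitivity (Sample Size Calculations): 1.96² × 0.9 × 0.1 / 0.1² = 34.57 ROSC cases; 34.57 / 0.40 = 86.4, so 87; 87 / 0.95 = 91.6, so 92. Both stated figures reproduce. They concern sensitivity and specificity and do not bear on this point, except that 0.40 × 87 = 34.8 gives about 35 ROSC events for the regression.

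**Inputs.** The definition of ΔPI, the model, the covariates and the 40% ROSC prevalence come from the Protocol. ΔPI is read as later minus initial; the opposite order only flips the sign. The documents do not give the following, so they are assumed:

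- correlation ρ between initial and later PI: 0.3 to 0.7
- ratio k of later to initial SD: 0.8 to 2
- log-odds for ΔPI at a given initial PI: b_Δ = 1.0 per SD of initial PI
- log-odds for initial PI at a given ΔPI: b₀ = 0 to 2.5

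**Algebra.** In the linear approximation, the ΔPI slope without initial PI is

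b_Δ + b₀ × (ρk − 1) / (1 + k² − 2ρk).

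At k = 1 the multiplier is (ρ − 1) / (2 − 2ρ) = −0.5 for any ρ. The slope is then attenuated whenever b₀ > 0, and reversed only when b₀ exceeds 2 × b_Δ. The sign of the multiplier is the sign of ρk − 1, so initial PI and ΔPI are negatively correlated only when ρk < 1.

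**Simulation.** Logistic fits with 200,000 patients per scenario and 40% ROSC, for b_Δ = b₀ = 1.0:

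| k | ρ | multiplier | ΔPI coefficient without initial PI | with initial PI |
|---|---|---|---|---|
| 1 | 0.3 | −0.50 | 0.43 | 1.00 |
| 1 | 0.5 | −0.50 | 0.45 | 1.01 |
| 1 | 0.7 | −0.50 | 0.42 | 0.99 |
| 1.5 | 0.3 | −0.23 | 0.66 | 1.00 |
| 1.5 | 0.5 | −0.14 | 0.73 | 1.01 |
| 1.5 | 0.7 | +0.04 | 0.88 | 0.99 |
| 2 | 0.5 | 0.00 | 0.85 | 1.00 |
| 2 | 0.7 | +0.18 | 1.02 | 1.01 |

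Part of the shortfall is not confounding. An odds ratio shrinks when any prognostic covariate is left out, even an uncorrelated one. That explains 0.85 where the multiplier is zero, and about 0.44 rather than 0.5 at equal SDs.

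**Varying the level effect** at k = 1, ρ = 0.5: the coefficient without initial PI is 1.00, 0.72, 0.45, 0.19 and −0.15 for b₀ = 0, 0.5, 1, 1.5 and 2.5. Over all 48 scenarios with b₀ > 0, 38 were attenuated, 8 reversed and 2 not attenuated. All 8 reversals had k of 1 or less. With b₀ = 0 there was no bias.

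**Power at n = 87** (k = 1, b_Δ = b₀ = 1.0, without the five listed covariates): about 60%, 47% and 30% without initial PI at ρ = 0.3, 0.5 and 0.7, against 97%, 94% and 85% with it. At k = 1.5 the gap nearly disappears: 99%, 97% and 99% against 100%, 100% and 98%. Part of that is the larger signal at k = 1.5.

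**The case against.** Several objections have force.

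- **The list is open.** A reader might infer that the plan excludes initial PI. It does not; initial PI is merely unnamed, and a separate analysis plan could add it. But the Protocol's own analysis section states the exposure, the model and five named covariates, calls the confounders predetermined, and gives no assurance that initial PI will be among them.
- **The adjusted coefficient answers a different question.** With later PI F and initial PI I, b(F − I) + cI = bF + (c − b)I. The ΔPI coefficient given initial PI is therefore the later-PI coefficient given initial PI. The case b_Δ = b₀ is exactly the one in which only later PI matters, so the recovered 1.0 does not show that trend adds anything beyond the final level. This stands and governs the interpretation. The unadjusted change score is a legitimate description of goal 2, but it does not separate change from starting level.
- **The negative correlation is not guaranteed.** A reader might infer that patients who start high must score low on ΔPI by construction. That requires ρk < 1 and fails if PI spreads enough during resuscitation.
- **Reversal is an extreme case.** A reader might infer that the trend effect will change sign. If initial PI alone mattered (ρ = 0.5, equal SDs), the unadjusted odds ratio would be 0.65, but that contradicts the sponsor's expectation that a rising PI helps.
- **Between-patient variation may be nuisance.** If PI levels differ for reasons unrelated to prognosis, subtracting the patient's own start removes that variation, the unadjusted coefficient is unbiased, and adjustment costs some power (91% to 83% at k = 1, ρ = 0.7). The Protocol's remark that PI varies between patients fits this reading too.
- **The simulations omit the five listed covariates.** Some of these may absorb part of initial PI's prognostic effect, so the residual bias could be smaller.

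These points limit the size and meaning of the bias. They do not make the model without initial PI the better choice when the sponsor expects level and trend both to matter.

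**Conclusion.** The point holds in a limited form. As written, the model does not ensure that the change in PI is separated from its starting level. Bias toward zero rests on two conditions: similar spread of initial and later PI, and an effect of initial PI on ROSC at a given ΔPI. The sponsor's expectation makes the second plausible; the documents are silent on the first. Under the assumed effects the coefficient ranges from less than half its true value at equal SDs to no attenuation at correlation 0.7 with SD ratio 2. At equal SDs, reversal needs a level effect about twice the trend effect or more, and somewhat less if later PI is less spread than initial PI.

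The documents do not support a claim that the trend result will be wrong in sign, or that the sensitivity, specificity and AUC analyses or the sample size are compromised. The correction is worth making before analysis because it concerns a stated goal and needs no new data.

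**What to change.** Name initial PI as a continuous covariate in the ΔPI regression, log-transformed if skewed; in that case take ΔPI on the log scale as well, so that the two terms stay on one scale. Close the covariate list at the same time. Report the ΔPI coefficient as the effect of the change at a given starting PI, and say that this is the same as the effect of later PI given initial PI. The unadjusted association can be shown beside it as a description.

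No new measurement is needed, since every patient with a ΔPI has an initial PI. Counting initial rhythm as one binary term, the model grows from six parameters to seven, and events per parameter fall from 34.8 / 6 = 5.8 to 34.8 / 7 = 5.0. That is already few, which is a further reason to fix the list now. There is also a small loss of power if initial PI has no effect of its own.

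### The final-value strand of the PI-versus-ETCO₂ comparison has no pre-ROSC cut-off, so it may partly measure detection of ROSC; the other strands and the primary endpoint are unaffected

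*Protocol*

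**What the plan says.** The Secondary Endpoints paragraph of the Protocol's statistical analysis plan section sets out a superiority analysis of PI against ETCO₂, with ROC curves compared by DeLong's method. It has three strands. Two are in one sentence: "Initial and final values of both PI and ETCO₂ will be assessed for their ability to predict ROSC". The third follows: "Moreover averaged values per 2 min cycle will be assessed for their ability to predict ROSC in the following cycle". No strand is named as the basis for the superiority claim.

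The Primary Endpoint paragraph just before it fixes the reading time for ΔPI, as the difference "between initial PI and PI values of the cycle preceding ROSC or the last cycle in the absence of ROSC".

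On recording, Methods (Study Design) says of PI: "Monitoring of perfusion index will be initiated as soon as possible and recorded until the end of the resuscitation efforts". Of the other signal it says: "ETCO₂ will be placed as soon as possible and recorded until the end of the resuscitation". Data collection and reporting adds: "Data will be collected throughout the intervention up until death or hospital admission or intensive care admission whichever comes first". The Tertiary Endpoints paragraph needs PI values from after ROSC: "As a tertiary endpoint we will study the predictive value of PI to predict further re-arrest following a ROSC".

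**The concern.** A predictor has to be read before the event it predicts. In a patient without ROSC, the last recorded value is always a value under compressions. In a patient with ROSC, the last recorded value may be taken once a spontaneous pulse is back. The Protocol describes PI as a measure of pulsatile strength, so a returned pulse would enter the marker directly. ETCO₂ may also change when circulation returns. The predictor would then partly contain the outcome.

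There is a second route. If a patient has ROSC, re-arrests and dies, the last recorded value comes from the later arrest while the patient still counts as having had ROSC.

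At stake is the meaning of one of the three comparisons behind the superiority question. If the two signals respond differently to ROSC, a DeLong test on final values would partly compare those responses and not predictive ability. The two signals also start separately, each as soon as possible, and nothing says that their initial or final values come from the same cycle.

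**Working it through.** **1. The Protocol's own figure.** The only figure given is the sample size, and it reproduces. For sensitivity: 1.96² × 0.90 × 0.10 / 0.10² = 34.57 patients with ROSC; 34.57 / 0.40 = 86.4, rounded up to 87; 87 / 0.95 = 91.6, rounded up to 92. This point concerns when a predictor is read and does not change that number.

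**2. Reading time of each predictor.**

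| Analysis | Reading time in the Protocol | Before ROSC? |
|---|---|---|
| Primary, PI by cycle | 2-minute average, tested against ROSC in the next cycle | Yes |
| Primary, ΔPI | "PI values of the cycle preceding ROSC or the last cycle in the absence of ROSC" | Yes |
| Secondary, initial values | Start of each recording | Yes, by position |
| Secondary, 2-minute averages | Tested against ROSC in the next cycle | Yes |
| Secondary, final values, PI and ETCO₂ | Not stated | Not ensured |

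**3. Do later values exist?** For PI, yes: the tertiary endpoint cannot be analysed without values after ROSC. For ETCO₂, recording runs to the end of resuscitation, so a reading at or around ROSC is possible. The text therefore permits a final value at or after ROSC. It does not require one.

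**4. Illustration of size.** The inputs here are assumptions, not figures from the Protocol: normally distributed markers with equal variance; δ, the true separation in SD before ROSC; f, the share of ROSC patients whose final value is misread; d, the shift in those values in SD.

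AUC = (1 − f) × Φ(δ/√2) + f × Φ((δ + d)/√2)

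*A marker with no predictive value* (δ = 0, true AUC 0.50):
- d = 1, f = 50%: 0.5 × 0.50 + 0.5 × 0.760 = 0.63
- d = 1, f = 100%: 0.76
- d = 2, f = 100%: 0.92

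*Two markers, both with true AUC 0.65* (δ = 0.545):
- f = 50%: d = 2 gives 0.5 × 0.65 + 0.5 × 0.964 = 0.81; d = 1 gives 0.5 × 0.65 + 0.5 × 0.863 = 0.76
- f = 100%: 0.96 and 0.86

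The gap appears although the markers predict equally well. It favours whichever signal rises more. Swapping the two shifts reverses it, and equal shifts remove it.

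*Re-arrest route.* Suppose instead that the final value comes from a later, fatal arrest and is lower by 1 SD (d = −1) in f = 25% of ROSC patients, with true AUC 0.65: 0.75 × 0.65 + 0.25 × Φ((0.545 − 1)/√2) = 0.4875 + 0.25 × 0.374 = 0.58. The AUC falls.

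The two routes pull in opposite directions, and the Protocol gives no value for f, d or the re-arrest rate.

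**The case against.** The strongest reply is that this is an undefined term and not a stated error. One paragraph earlier, initial PI is paired with the cycle before ROSC, and *initial and final* reads naturally as the same pair. The Study Summary gives the study parameter as PI during cardiac arrest, its purpose statement refers to PI under chest compressions, and the first two goals speak of values during resuscitation. A separate analysis plan, not shown, could also fix the window.

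Much of this stands. A pre-ROSC reading may well have been intended. But the statements about arrest and compressions concern PI, the anchor is written only for ΔPI, and nothing equivalent exists for ETCO₂. The Protocol's own analysis section names the final value as a predictor, and applying those words literally to the recordings gives a contaminated strand.

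A reader might go further and infer that the secondary comparison measures detection and not prediction, that both AUCs must be inflated, or that a finding of PI superiority could arise from this alone. The documents do not support any of these. Two of the three strands are ordered in time and would be reported alongside. The re-arrest route lowers the AUC. A spurious gap in favour of PI needs PI to respond more strongly than ETCO₂, and the Protocol has no figure on that.

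**Conclusion.** The concern holds for one strand only. As worded, the final-value comparison does not ensure that PI and ETCO₂ are read before ROSC, although the Protocol sets exactly that limit for ΔPI. Its AUCs and their DeLong difference may therefore partly reflect the response to ROSC. Size and direction cannot be established from the documents; the figures above show only that plausible-looking assumptions can move an AUC by several hundredths or much more.

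The initial-value strand, the next-cycle strand, the primary endpoint and the sample size are unaffected. This should be fixed before analysis, but as a clarification to part of a secondary endpoint it does not undermine the study.

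**What to change.** In Secondary Endpoints, define the final value, for both PI and ETCO₂, as the 2-minute average of the last complete cycle preceding the first ROSC, or of the last complete cycle if there is no ROSC. Read both signals from the same cycle. This extends the existing ΔPI rule to both signals, and tying it to the first ROSC also settles the re-arrest case.

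State that the superiority claim rests on the next-cycle or the initial-value comparison. Even with the cut-off, the timing of the final value depends on the outcome, so that strand is better treated as supportive.

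The cost is wording; the recordings should already hold the values. Patients with ROSC before any complete paired cycle drop out of this strand, and its AUCs may be less favourable.
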